## **1.0 INTRODUCTION**

### **1.1 Study objectives**

Primary Objective: To evaluate the response rate and toxicity of the combination of mitoxantrone, etoposide and gemtuzumab ozogamicin as second line therapy in patients with acute myeloid leukemia (AML) who have failed the first induction therapy.

Secondary Objectives: To assess the progression-free survival, overall survival and treatment related mortality in patients with AML treated with the combination of mitoxantrone, etoposide and gemtuzumab ozogamicin.

To explore if age, cytogenetic status, percent of blast in the bone marrow prior to therapy or percent expression of CD33 in the leukemia blasts are predictive of complete remission, overall survival or progression-free survival in patients with AML treated with the combination of mitoxantrone, etoposide and gemtuzumab ozogamicin.

### **1.2 Background and Rationale**

Acute myeloid leukemia (AML) is a disease characterized by a clonal proliferation of myeloid precursors with reduced capacity to differentiate into more mature cellular elements. As a result, there is an accumulation of leukemic forms in the bone marrow, peripheral blood and other tissues, with a marked reduction in red cells, platelets, and neutrophils. The increased production of malignant cells, along with reduction in these mature elements, results in a

variety of systemic symptoms and signs. These include anemia, bleeding and an increased risk of infection. If left untreated, AML can lead to death within weeks.

The standard treatment for newly diagnosed AML has not changed appreciably over the last few decades and consists primarily of an anthracycline (e.g. daunorubicin, idarubicin) combined with a nucleoside analogue, cytarabine. The goal of remission induction chemotherapy is the rapid restoration of normal bone marrow function. Obtaining complete remission (CR) varies substantially depending on several factors, most notably age and cytogenetic abnormalities at the time of AML diagnosis. CR rates of 65-80% can be expected in younger patients (variably defined as < 55-60 years). CR rates decrease to 30% to 50% in older patients.

There is no agreed standard of care for AML patients that do not respond to initial first line induction therapy. Although remission after second-line therapy may occur, the CR rate is considerably lower. A number of chemotherapy regimens have been used in patients with resistant disease with overall CR rates of 20-40%. These regimens include different combinations and doses of agents that are effective in the treatment of AML such as fludarabine, cytarabine, etoposide, and mitoxantrone.

Gemtuzumab ozogamicin (GO) is an antibody drug conjugate consisting of a recombinant humanized antibody to CD33 which is linked to calicheamicin. Calicheamicin is a potent antitumor antibiotic that cleaves double-stranded DNA at specific sequences. Approximately 90% of AML patients have myeloid blast cells expressing the CD33 surface antigen. Monotherapy with GO resulted in CR of 20-25% in adults with CD33 positive AML in first relapse. GO was approved by the United States Food and Drug Administration (FDA) for use in patients age 60 or older with CD33+ AML in first relapse who were not considered candidates for cytotoxic chemotherapy in 2000^9. However, due to early deaths in a prospective phase 3 randomized study which incorporated GO in the induction phase in one of the arms (SWOG S0106) the manufacturer withdrew the product from the American market in 2010. The SWOG S0106 study used 6 mg/m^2 of GO on day 4 of induction with cytarabine, daunorubicin. The treatment-related mortality (TRM) was 5% on the GO arm vs 1% on the other arm. In 2017, FDA again approved GO for induction therapy in combination with chemotherapy based on a phase 3 prospective randomized, open-label study (ALFA-0701 trial) and as monotherapy for patients unfit for intensive treatment based on the phase 3

randomized EORTC-GIMEMA AML-19 trial. The ALFA-0701 trial randomized 280 patients 50-70 year-old to receive induction with daunorubicin and cytarabine or daunorubicin, cytarabine and GO 3mg/m^2 on days 1,4,7 of induction. It showed that the addition of GO to the induction chemotherapy improved event-free survival. The AML-19 trial randomized 237 patients unfit for induction chemotherapy to receive either best supportive care or GO 6mg/m^2 on day 1 and 3mg/m^2 on day 8. It showed that GO improved the overall survival in patients unfit for intensive treatment when compared to best supportive care with no difference in the adverse events. The NCRI AML17 trial studied further the dose of GO with induction chemotherapy showing that 3mg/m^2 has the same efficacy but better safety profile than 6mg/m^2. The dosing regimen of GO as it is currently approved by the US FDA is 3mg/m^2 (maximum dose 4.5mg) on days 1,4,7 with induction chemotherapy or 6mg/m^2 on day 1 followed by 3mg/m^2 on day 8 if used as monotherapy.

The most important GO-associated hematologic toxicity is myelosuppression (thrombocytopenia, neutropenia). Infusion-related adverse reactions are similar to those of other monoclonal antibodies (fever, chills, cutaneous rash, hypotension, hypertension, dyspnea, nausea, emesis and headache). They are usually transient and respond well to symptomatic therapy.

Hepatic veno-occlusive disease or sinusoidal obstructive syndrome (VOD/SOS) is the most frequently reported life-threatening non-hematological adverse event. Overall, among all adult GO- treated AML patients evaluated in the clinical trial setting, SOS occurred at a rate of 3% when GO was administered as monotherapy at the initial FDA approved dose and schedule (for relapsed AML, 9 mg/m^2 on day 1 and 14); 7% when the drug was used in conjunction with other chemotherapeutic agents that are not known to be hepatotoxic; and 28% when GO was combined with thioguanine, a hepatotoxic chemotherapeutic agent. SOS rates were between 15% and 40% if stem cell transplantation was performed within 3 months of GO administration. Another observational study showed an overall 9.1% risk of SOS with GO and 2.7% risk of death from SOS. During the early 2000s when GO was used at higher doses it was observed that patients that received GO <3.5 months before allogeneic stem cell transplantation had much higher incidence of SOS, which was no longer observed in the modern era of lower GO fractionated doses.

Various clinical trials have evaluated the efficacy of GO as monotherapy in newly-diagnosed AML, refractory/relapsed AML and in combination with chemotherapy for induction. Different dosing schedules of GO were used in these trials. In addition to grade 3/4 neutropenia and thrombocytopenia some patients also develop transaminitis and VOD (Table 1).

**Table 1:** Clinical trials with gemtuzumab ozogamicin

Trial	No. of pts	State of disease	GO Dosing	Therapy	Results	Ref
EORTC-GIMEMA AML-19	237	New diagnosis, unwilling or unfit for treatment	Induction: 6 mg/m  on day 1 and 3 mg/m  on day 8. Maintenance: 2mg/m  monthly up to 8 doses	Best Supportive Care GO +/-	CR/CRI 27% on the GO arm. OS improvement at 1 year with GO (4.9 vs 3.6 months, p=0.005)	12
LRF AML 14 and NCRI AML 16	495	New diagnosis, unfit for intensive treatment	5 mg (fixed dose) on day 1 of 42-day cycles for a maximum of four cycles	LDAC 20mg BID on days 1-10 of 42-day cycles +/- GO	Improved CR with GO (21% vs 11%, P= .002). No difference in OS. Patients in the GO arm had more nausea and vomiting, required more platelet transfusions and longer duration of antibiotics. No episodes of VOD were reported.	19
MRC AML-15	1113	New diagnosis	3mg/m  on the first day of induction.	DA or DAE or FLAG-IDA +/- GO	No difference in OS but improved 5-year OS in patients with favorable cytogenetics. No excess hematologic or liver toxicity on the GO arm	20
ALFA-0701	278	New diagnosis	Induction: 3mg/m  on days 1,4,7 Consolidation: 3mg/m  on day 1 for up to two cycles	Induction DA +/- GO Consolidation: DA +/- GO	Improved EFS, DFS on the intervention arm but no difference in OS. Prolonged thrombocytopenia and neutropenia on the GO arm.3 cases of VOD were reported on the GO arm.	11,21
NCRI AML16	1115	New diagnosis	Induction: 3 mg/m  on day 1	DA +/- GO	Improved OS on the treatment arm and similar TRM	22
SWOG S0106	595	New diagnosis	Induction 6 mg/m  on day 4	DA (with D at 60 mg/m  ) vs DA (with D at 45mg/m  ) plus GO	No difference in OS with increased TRM in the GO arm (6% vs 1%)	10

EORTC-GIMEMA AML-17	472	New diagnosis	Induction: 6mg/m  on days 1 and 15	MEC +/- GO	Similar CR rate and OS. Higher TRM with GO (22% vs 18%) mainly driven by patients >70 years old	23
NCRI	788	New diagnosis	Induction: randomization To 3 or 6 mg/m 	Randomization	No difference in OS. Increased TRM with higher	13
AML17			on day 1	to ADE or DA, both + GO	GO dose.	
HOVON-43	232	Consolidation	6 mg/m  every 4 weeks, up to 3 cycles	Observation vs GO	No difference in OS	24

**Abbreviations:** CR, complete remission; CRi, complete remission with incomplete hematologic recovery; GO, Gemtuzumab Ozogamicin; OS, overall survival; LDAC, low-dose cytarabine; VOD, veno-occlusive disease, DA, daunorubicin + cytarabine, DAE, daunorubicin + cytarabine + etoposide; FLAG-IDA, fludarabine + cytarabine + G-CSF + idarubicin; EFS, event-free survival; DFS, disease-free survival; TRM, treatment-related mortality; MEC, mitoxantrone + etoposide + cytarabine; ADE, cytarabine + daunorubicin + etoposide

### Rationale

The combination of mitoxantrone and etoposide is an active regimen in refractory/relapsed AML patients. In a retrospective study, we evaluated the efficacy and toxicity of mitoxantrone and etoposide in AML patients treated at our institution who did not respond to first induction therapy with cytarabine and an anthracycline. A total of thirty-five AML patients were treated with mitoxantrone (10 mg/m^2/d) on days 1-5 and etoposide (100 mg/m^2/d) on days 1-5. Thirteen of thirty-five patients (37%) achieved CR. There were no grade 3/4 hepatic toxicities. The median duration of neutropenia in patients achieving CR was 29 days after reinduction. 14% of patients died from infectious complications.

In order to increase the efficacy of mitoxantrone and etoposide as second line therapy in patients with AML we propose to conduct a phase II clinical trial evaluating the safety and efficacy of the combination of GO, mitoxantrone and etoposide. A similar trial was open in our institution before Pfizer withdrew the drug from the market in 2010^26. Before the withdrawal 5 patients were treated with a regimen consisted of mitoxantrone 10 mg/m^2 administered intravenously on days 1–3, etoposide 100 mg/m^2 administered on days 1–5 and on day 6 GO 3 mg/m^2. Three of the five patients achieved a CR. There were no treatment-related deaths. All patients developed grade 3–4 neutropenia and thrombocytopenia, with complete responders requiring a median of 19 days (range, 17–34 days) from the completion of

treatment to recover their neutrophils and a median of 24 days (range, 17–34 days) to recover their platelets. One patient developed grade 3 ALT transaminitis that resolved within 24 h and one patient developed a transient ischemic attack. No patient developed clinical signs or symptoms of veno-occlusive disease.

It has been demonstrated that high peripheral CD33-antigen load is an independent adverse prognostic factor in AML patients treated with GO. Data indicate that a high peripheral CD33antigen load consumes a large portion of the GO, which results in reduced GO penetration into the bone marrow . As a consequence, CD33 saturation of AML blast cells present in the bone marrow is incomplete, which may hamper subsequent cell kill. Administration of GO may be more effective after reduction of the leukemic cell burden with conventional chemotherapy. Thus, we plan to administer the GO after the administration of mitoxantrone and etoposide. Furthermore, since enrolled patients in the study will already be treated with combination of cytarabine and an anthracycline (1st regimen) and mitoxantrone and etoposide (2nd regimen) and GO has been associated with neutropenia and thrombocytopenia, we plan to use a single dose of GO 3 mg/m^2 the day after the completion of the 5 days of etoposide and mitoxantrone.

## **2.0 ELIGIBILITY ASSESSMENT AND ENROLLMENT**

### **2.1 Eligibility Criteria**

1. Able to understand and have the ability to provide written consent.
2. Age:  $\geq 18$  and  $\leq 75$  years old.
3. Patients with newly diagnosed AML based on the World Health Organization classification who have persistent disease after their first course treatment with an anthracycline and cytarabine (the diagnosis of persistent disease, which is defined as  $\geq 10\%$  blasts by morphology for this trial or  $>5\%$  blasts if they have had an increase in blasts from the last bone marrow biopsy, will be based on their assessment after bone marrow aspiration and/or biopsy after initial treatment). The bone marrow aspiration and/or biopsy will be evaluated by the Hematopathology Division of the University of Pittsburgh. In order to prevent any delays in starting therapy for eligible patients, a preliminary evaluation of the bone marrow will be sent by the hematopathologist via e-mail to the investigator.

4. Patients with myelodysplastic syndrome (MDS) based on the World Health Organization classification who have persistent disease after their treatment with an anthracycline and cytarabine (the diagnosis of persistent disease, which is defined as  $\geq 10\%$  blasts by morphology for this trial or  $>5\%$  blasts if they have had an increase in blasts from the last bone marrow biopsy, will be based on their assessment after bone marrow aspiration and/or biopsy after initial treatment).
5. CD33 expression in  $\geq 30\%$  of leukemic blasts on the bone marrow.
6. Eastern Cooperative Oncology Group Performance Status of 0 -2 (see Appendix I).
7. Patients must have the following laboratory values prior to beginning protocol treatment:
  - Calculated creatinine clearance  $\geq 30$  mL/min (using the Cockcroft-Gault equation CL creatinine =  $((140\text{-age}) \times \text{body mass} \times 0.85 \text{ if female}) / (72 \times \text{creatinine})$  where age is given in years, body mass is given in Kg and creatinine is given in mg/dl).
  - Aspartate aminotransferase (AST)  $\leq 2.5 \times$  upper normal limit.
  - Alanine aminotransferase (ALT)  $\leq 2.5 \times$  upper normal limit.
  - Total bilirubin  $\leq 2 \times$  upper normal limit.

**Note:** As many eligible patients will be pancytopenic secondary to their disease or prior treatments, hematologic abnormalities will not be used as criteria for entry or exclusion.

8. Left ventricular ejection fraction (LVEF)  $\geq 50\%$ .
9. Females of child-bearing potential must have a negative pregnancy test during screening and all subjects must agree to use an effective method of contraception. A woman is eligible to enter and participate in the study if she is of:
  - a. Non-childbearing potential (*i.e.*, physiologically incapable of becoming pregnant) including any female who has had a hysterectomy or has had a bilateral oophorectomy (ovariectomy).
  - b. Childbearing potential, has a negative serum pregnancy test during the screening period and agrees to avoid sexual activity or use contraception from screening through follow-up (method of birth control if the patient is not neutropenic include the use of a diaphragm, intrauterine device, contraceptive sponge and/or usage of male condom with a spermicide from the partner). A man with a female partner of childbearing potential is eligible to enter and participate in the study if he has either had a prior vasectomy or agrees to avoid sexual activity or use adequate contraception (as described above) from screening through follow-up.

## **2.2 Exclusion criteria**

1. Patients with a diagnosis of Acute Promyelocytic Leukemia (APL) as defined by the World Health Organization.
2. Relapsed acute leukemia.
3. Bi-lineage or bi-phenotypic leukemia.
4. Prior use of mitoxantrone or etoposide or GO.
5. Previous allogeneic hematopoietic cell transplantation.
6. First induction course of acute myeloid leukemia with CPX-351.
7. Has a history or current evidence of any condition, therapy, or laboratory abnormality that might confound the results of the trial, interfere with the subject's participation for the full duration of the trial, or is not in the best interest of the subject to participate, in the opinion of treating investigator.
8. Has known history of active Hepatitis B (HBsAg reactive) or Hepatitis C (detectable HCV RNA).
9. Uncontrolled, life-threatening infection that is not responding to antimicrobial therapy.
10. Has known psychiatric or substance abuse disorders that would interfere with cooperation with the requirements of the trial.
11. Patient may have not received any other investigational anti-neoplastic agents within 4 weeks from the start of therapy.
12. Concurrent active malignancy; exceptions include patients who have been disease free for 5 years, patients with a history of completely resected non-melanoma skin cancer or successfully treated in situ carcinoma, or patients with another malignancy with better prognosis than AML.
13. Women who are pregnant or breastfeeding.
14. Evidence of severe or uncontrolled systemic diseases (e.g., unstable or uncompensated respiratory or cardiac disease).

## **2.3 Eligibility evaluation**

The following clinical and laboratory assessments must be performed for all eligible patients within 14 days of study enrollment and consent:

1. Complete medical history and physical examination, including height, weight, body surface area (BSA), ECOG performance status, and a neurological evaluation.
2. Echocardiogram to evaluate cardiac ejection fraction.
3. CBC with differential and platelets.
4. Complete metabolic panel (Na, K, Cl, CO2, glucose, BUN, Cr, Ca, total protein, albumin, total bilirubin, AST, ALT, and alkaline phosphatase) and magnesium level.
5. LDH, uric acid, and phosphorus levels.
6. PT/INR, PTT.
7. Urinalysis.
8. PA and lateral chest x-ray. If clinically indicated CT Chest/Abdomen/Pelvis can be performed.
9. EKG.
10. Urine pregnancy test for all women  $\leq$  60 years old.

The following clinical and laboratory assessments must have been performed for all eligible patients within 12 weeks from initiation of treatment:

1. Hepatitis B surface antigen.
2. Hepatitis C antibody and if positive HCV RNA.

## **3.0 STUDY IMPLEMENTATION**

### **3.1 Study design and treatment plan**

This study is an open-label, single arm phase II study which will examine the efficacy and toxicity of the combination therapy of GO, mitoxantrone and etoposide in patients who did not respond to first line induction therapy.

#### **Treatment plan**

Eligible patients will be treated at the UPMC Hillman Cancer Center inpatient leukemia service. Patients will receive mitoxantrone 10mg/m^2 administered intravenous piggyback

(IVPB) in 50ml 0.9% normal saline over 15 minutes on days 1-5 and etoposide 100 mg/m^2 administered intravenously in 500 ml of 0.9% sodium chloride over 2 hours on days 1-5.

On day 6, patients will receive a single dose of GO 3mg/m^2 (maximum dose 4.5mg). Patients will be pre-medicated 1 hour prior to the GO infusion with diphenhydramine 50mg administered orally or intravenously, acetaminophen 650 mg administered orally or intravenously and 1mg/kg methylprednisolone or an equivalent dose of alternative corticosteroid administered IV within 30 minutes prior to infusion of GO. GO will be administered intravenously in 50 ml (or other suitable volume resulting in a final GO concentration between 0.075 mg/mL to 0.234 mg/mL) of 0.9% sodium chloride over 2 hours. Doses of GO will be based on BSA calculated using actual body weight with a cap of 4.5mg. Vital signs will be recorded within one hour prior to the infusion and then every 30 minutes during the infusion and 30 minutes and one hour after completion of infusion. An additional dose of methylprednisolone 1 mg/kg IV may be given for any sign of infusion reaction, such as fever, chills, hypotension, or dyspnea occurring during the GO infusion or within 4 hours after the GO infusion.

For dose modifications based on kidney and liver function please see the treatment schema at the end of the study.

Supportive care including blood product transfusions, antiemetic medications, antiviral and antifungal medications, growth factor support, tumor lysis syndrome prophylaxis, or empiric antibiotics may be used at the clinical discretion of the provider.

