## **8. STUDY EVALUATION, TREATMENT SCHEMA AND FLOW CHART**

Pre-treatment evaluation	
	Within last 6 weeks from day of consent
Anti-Hepatitis C antibody and if positive HCV RNA PCR	X

Hepatitis B surface antigen	X
	Within 14 days from day of consent
Medical history and physical examination	X
Height, weight, BSA, ECOG performance status	X
Toxicities from prior therapies	X
Cardiac echocardiogram	X
Bone marrow biopsy and aspiration	X
Urine $\beta$ HCG in women $\leq$ 60 years old (pregnancy test)	X
PT/INR, PTT	X
Complete metabolic panel (Na, K, Cl, CO 2 , glucose, BUN, Cr, Ca, total protein, albumin, total bilirubin, AST, ALT and alkaline phosphatase)	X
Magnesium, Phosphorous, Uric Acid, LDH	X
CBC with differential	X
Urinalysis	X
Electrocardiogram (12 lead)	X
Chest radiograph	X
CT Chest, Abdomen and/or Pelvis if indicated	X

Treatment Schema						
	Day 1	Day 2	Day 3	Day 4	Day 5	Day 6
Mitoxantrone	X	X	X	X	X	
Etoposide *	X	X	X	X	X	
Gemtuzumab ozogamicin **						X

\* Dose modification of etoposide for patients who develop elevated total bilirubin and/or AST or decrease in creatinine clearance

Adverse event	Dose modification of etoposide
CrCl 10 – 50 ml/min	administer 75% of normal dose
CrCl < 10 ml/min	administer 50% of normal dose
CrCl <50 ml/min AND Total bilirubin >3 mg/dL or AST >3 times ULN	Hold etoposide

\*\*If enrolled patients on day 6 of therapy have levels of aspartate aminotransferase (AST)  $\geq 2.5 \times$  UNL or alanine aminotransferase (ALT)  $\geq 2.5 \times$  UNL or total bilirubin  $\geq 2 \times$  ULN the administration of GO will be on hold until recovery of total bilirubin to less than or equal to  $2 \times$  ULN and AST and ALT to less than or equal to  $2.5 \times$  ULN prior to each dose. Daily values of LFTs will be obtained. The GO dose can be delayed up to the 10th day after the initiation of therapy due to toxicity or unexpected events (ie infection). Doses of GO will be capped at 4.5mg. Administration of a FLT3 inhibitor will be prohibited until CR is achieved. The use of a FLT-3 inhibitor is not prohibited after CR has been achieved for patients with FLT3-ITD or FLT-TKD mutations.

ON STUDY EVALUATION	TIMING
History and physical examination	Daily during the hospital stay at UPMC Shadyside Hospital and then weekly as outpatient for 4 weeks, and then every 2 weeks until count recovery

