## **Etoposide**

**Other Names:** Toposar

**Classification:** Podophyllotoxin Derivative

**Mechanism of Action:** Etoposide has been shown to delay transit of cells through the S phase and arrest cells in late S or early G2 phase. The drug may inhibit mitochondrial transport at the NADH dehydrogenase level or inhibit uptake of nucleosides into HeLa cells. It is a topoisomerase II inhibitor and appears to cause DNA strand breaks. Etoposide does not inhibit microtubular assembly.

**Storage and Stability:** Unopened vials of etoposide are stable for 24 months at room temperature (25 degrees Celsius). Vials of etoposide are stable at room temperature for 96

hours when diluted to concentrations of 0.2 milligrams/milliliter (mg/mL); stability is 24 hours with concentrations of 0.4 mg/mL at room temperature. The manufacturer does not recommend that etoposide be administered at concentrations greater than 0.4 mg/mL because time to precipitation is highly unpredictable and precipitate formation has been reported to occur earlier than the utility times listed above. Etoposide 20 mg/ml is stable in a plastic syringe for 5 days when stored at room temperature under fluorescent light.

**Dose Specifics:** Patients will receive etoposide 100 mg/m^2 administered intravenously in 500 ml of 0.9% sodium chloride over 2 hours on days 1-5 (for patients who have elevated total bilirubin, AST or reduced creatinine clearance during the etoposide infusion see treatment schema for dose modification of the etoposide). BSA will be calculated based on actual body weight.

**Preparation:** Etoposide Injection must be diluted prior to use with either 5% Dextrose Injection, or 0.9% Sodium Chloride Injection, to give a final concentration of 0.2 to 0.4 mg/mL . If solutions are prepared at concentrations above 0.4 mg/mL, precipitation may occur. Parenteral drug products should be inspected visually for particulate matter and discoloration prior to administration whenever solution and container permit.

**Route of Administration:** Etoposide should be given as a diluted solution via the IV route.

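### At full dose, the fixed 500 mL etoposide volume breaks the protocol's own 0.4 mg/mL limit once body surface area passes about 2.0 m²

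*Combined protocol and SAP*

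**What the plan says.** The treatment plan in section 3.1 sets etoposide at 100 mg/m² daily, "administered intravenously in 500 ml of 0.9% sodium chloride over 2 hours on days 1-5". The etoposide entry in section 9 (Dose Specifics) repeats that dose and volume and adds that "BSA will be calculated based on actual body weight". Neither place caps the etoposide dose or the BSA, and neither allows another volume.

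The Preparation paragraph of the same entry makes dilution mandatory, "to give a final concentration of 0.2 to 0.4 mg/mL", and warns: "If solutions are prepared at concentrations above 0.4 mg/mL, precipitation may occur". The Storage and Stability paragraph agrees: "The manufacturer does not recommend that etoposide be administered at concentrations greater than 0.4 mg/mL because time to precipitation is highly unpredictable".

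The other two drugs are given some latitude. The GO order in section 3.1 names 50 mL "or other suitable volume resulting in a final GO concentration between 0.075 mg/mL to 0.234 mg/mL". The mitoxantrone Preparation text in section 9 treats 50 mL as a minimum and allows more.

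The dose-modification table in section 8 reduces etoposide for renal function. At a creatinine clearance of 10 to 50 mL/min the instruction is to "administer 75% of normal dose", and below 10 mL/min the dose is halved.

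**The concern.** A dose that scales with BSA in a volume that does not gives a concentration that rises with body size. The protocol also sets a ceiling on that concentration. If the ceiling falls within the range of ordinary adult BSA, the pharmacy has two written instructions that conflict for larger patients on each of the five etoposide days. Keeping to 500 mL produces a solution that section 9 says may precipitate. Keeping to the ceiling departs from a volume written in two places. What is at stake is the safety and consistency of a cytotoxic infusion. No estimate or test in the trial depends on it.

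**Working it through.** The protocol states no concentration or BSA threshold for etoposide, so there is no figure of its own to reproduce. The check compares the ordered dose and volume with the stated limit.

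**Inputs**
- Dose 100 mg/m², volume 500 mL: section 3.1 and section 9, Etoposide, Dose Specifics.
- Upper limit 0.4 mg/mL, lower limit 0.2 mg/mL: section 9, Etoposide, Preparation.
- Reduced doses of 75% and 50%: section 8.
- Stock strength 20 mg/mL: an assumption. Section 9 mentions this strength only for syringe stability ("Etoposide 20 mg/ml is stable in a plastic syringe for 5 days"). It is used only in the second reading below.

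**Reading A: 500 mL is the final volume.** Concentration = 100 × BSA / 500 = 0.2 × BSA mg/mL. Setting this to 0.4 gives BSA = 0.4 × 500 / 100 = 2.00 m².

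**Reading B: 500 mL is the diluent and the concentrate is added.** Concentrate volume = 100 × BSA / 20 = 5 × BSA mL, so concentration = 100 × BSA / (500 + 5 × BSA). Setting this to 0.4 gives 98 × BSA = 200, so BSA = 2.04 m².

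| BSA (m²) | Reading A (mg/mL) | Reading B (mg/mL) | Over the limit (A / B) |
|---|---|---|---|
| 1.8 | 0.36 | 0.354 | within |
| 2.0 | 0.40 | 0.392 | within |
| 2.1 | 0.42 | 0.411 | 5% / 3% |
| 2.2 | 0.44 | 0.431 | 10% / 8% |
| 2.4 | 0.48 | 0.469 | 20% / 17% |

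**Reduced doses.** At 75%, reading A gives 0.15 × BSA, which reaches 0.4 at 2.67 m². Reading B gives 200 / 73.5 = 2.72 m². At 50%, reading A gives 0.1 × BSA, which is below the 0.2 mg/mL lower limit when BSA is under 2.0 m². That last case should be rare, since entry requires a creatinine clearance of at least 30 mL/min.

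**Is a BSA above 2.04 m² unusual?** Eligibility sets no weight or BSA limit. As an illustration, by the Mosteller formula (assumed, since the protocol names none), 180 cm and 85 kg gives √(180 × 85 / 3600) = 2.06 m², above both crossings.

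**Volume that satisfies the limit.** Minimum final volume at full dose = 100 × BSA / 0.4 = 250 mL per m²: 500 mL at 2.0 m², 550 mL at 2.2 m², 600 mL at 2.4 m².

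**Comparison with GO.** The capped dose of 4.5 mg in 50 mL gives 0.09 mg/mL, inside its 0.075 to 0.234 mg/mL range. That order has a flexible-volume clause even so.

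**The case against.** The best defence is that the concentration range is itself a mandatory instruction in the protocol, with a safety reason attached, and stands in the same drug entry as the 500 mL order. A sensible pharmacist would treat 500 mL as the usual volume and use more for a larger patient, at one experienced inpatient leukemia service. Section 9 also requires a visual check for particles before administration. It lists 24 hours of stability at 0.4 mg/mL, against a 2-hour infusion. Just above the crossing the excess is only 3% to 5%, and patients on 75% dose are unaffected below 2.67 m². It is also fair to say that this is an internal inconsistency in a drug order and not a miscalculated figure.

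Most of this stands as a reason to think harm unlikely. It does not remove the conflict. The protocol has no rule of precedence, and a larger bag departs from the volume as written. Where the protocol wants a flexible volume it says so, as it does for GO. The visual check takes place before an infusion that runs for two hours, the listed stability times stop at 0.4 mg/mL, and the text itself calls the time to precipitation unpredictable above that.

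**Conclusion.** The concern holds. Read literally, the etoposide volume order contradicts the protocol's own concentration limit for full-dose patients with a BSA above 2.00 m² (final-volume reading) or 2.04 m² (diluent reading, assuming 20 mg/mL stock). The excess at 2.2 to 2.4 m² is 8% to 20%, depending on the reading. How many patients this affects cannot be stated from the documents. No harm is shown, and sample size, error rates and analysis are untouched. It is a real contradiction in a treatment order and worth correcting because the correction is small.

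**What to change.** In section 3.1 and in section 9 (Etoposide, Dose Specifics), keep 500 mL as the usual volume. After it, add the flexible-volume clause that the GO order already carries, with etoposide named and the range set to 0.2 to 0.4 mg/mL. The concentration range then governs. In practice the final volume at full dose is at least 250 mL per m² of BSA. The same clause covers the low-concentration case at the 50% dose.

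The cost is one clause in two places and a larger infusion for larger patients:

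| BSA (m²) | Minimum volume | Rate over 2 h | Extra over 5 days, reading A | Extra over 5 days, reading B |
|---|---|---|---|---|
| 2.2 | 550 mL | 275 mL/h | 5 × (550 − 500) = 250 mL | 5 × (550 − 511) = 195 mL |
| 2.4 | 600 mL | 300 mL/h | 5 × (600 − 500) = 500 mL | 5 × (600 − 512) = 440 mL |

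The present rate is 250 mL/h if 500 mL is the final volume. Pharmacy should confirm that the 2-hour duration remains acceptable at the larger volumes.
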